#### 10.0 Statistical Evaluation

We will enroll 20 patients in this exploratory study. We will first examine data from 5 patients to work out the logistical issues in the use of the imaging technology with the surgery as well as evaluation of safety. We will then examine data from the remaining patients in cohorts of 5. After each cohort of 5 patients we will review the logistics of the imaging technology and make adjustments deemed necessary to improve the surgical procedure. We will also evaluate safety.

Our primary objective is to determine the feasibility of acquiring *in-vivo* high-resolution microendoscopy (HRME) images of cervical adenocarcinoma in-situ (AIS) immediately prior to conization. We will use descriptive statistics to summarize the demographic and clinical characteristics of patients. We will estimate the proportion of patients for whom we can successfully acquire *in-vivo* HRME images of AIS immediately prior to conization with a 90% credible interval, assuming a beta(1.8, 0.2) prior distribution. This prior distribution is based on an anticipated success rate of 90%. If we complete the study with 18 patients for whom we can successfully acquire *in-vivo* HRME images of AIS, then our 90% credible interval will be 0.78 to 0.98. If we are able to successfully acquire in-vivo HRME images of at least 18 of the 20 patients enrolled in the study, then we will determine that the methodology is feasible.

Our secondary objective is to determine the accuracy of HRME images in distinguishing AIS from normal cervical tissue. We will tabulate AIS finding by the CKC specimen results as determined by pathology, and we will estimate the concordance of HRME images taken *ex-vivo* (as described in section 6.0) with pathology findings with a 90% credible, assuming a beta (1.8, 0.2) prior distribution for the concordance.

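### Does the Beta(1.8, 0.2) prior make the primary credible interval unsound if all 20 patients are imaged successfully?

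*Combined protocol and SAP*

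**What the plan says.** Section 10.0 (Statistical Evaluation) describes an exploratory study of 20 patients. The primary proportion is to be estimated "with a 90% credible interval, assuming a beta(1.8, 0.2) prior distribution". The reason given for the prior is "This prior distribution is based on an anticipated success rate of 90" percent. One example is worked: with 18 successes, "then our 90% credible interval will be 0.78 to 0.98".

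The decision rule is separate from the interval. Success in "at least 18 of the 20 patients enrolled in the study, then we will determine that the methodology is feasible". The same prior is used for the secondary endpoint ("assuming a beta (1.8, 0.2) prior distribution for the concordance"). No other prior, frequentist interval or sensitivity analysis to the prior appears in the document.

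**The concern.** An anticipated rate of 90% fixes only the mean of the prior. The shape of Beta(1.8, 0.2) is more optimistic than that description suggests: its median is 0.986, and 64% of its mass lies above 0.95 before any patient is imaged. Once a failure is observed, the data supply most of the failure count. With no failures, the posterior failure parameter stays at 0.2, and the lower limit depends visibly on that choice.

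The interval is the only planned statement of precision for the primary endpoint, and 20 of 20 is one of the three results that count as feasible. If the prior produced much of the apparent precision there, a reader could take a 20-patient study for a larger one.

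**Working it through.** **Inputs, all from section 10.0.** n = 20; prior Beta(1.8, 0.2); interval level 90%; feasibility at 18 or more successes. The type of interval is not stated. The comparators Beta(0.5, 0.5) and Beta(1, 1) are not in the document and are used here only as yardsticks.

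**Step 1: reproduce the plan's figure.** With x successes, a Beta(a, b) prior gives the posterior Beta(a + x, b + 20 − x). For x = 18 this is Beta(19.8, 2.2). Its 5% and 95% quantiles are 0.780 and 0.979, matching the stated 0.78 to 0.98. The highest-density interval would be 0.811 to 0.992, which does not match, so the planned interval is equal-tailed.

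**Step 2: check the prior against its stated basis.** Mean = 1.8 / (1.8 + 0.2) = 0.90, as stated. Weight = 1.8 + 0.2 = 2 patients, so its share of the posterior mean is 2 / 22 = 9%. At 20 of 20 the posterior mean is 21.8 / 22 = 0.991, slightly below the observed 1.00. The prior pulls the estimate down there, toward 0.90.

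**Step 3: compare equal-tailed 90% intervals.**

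| Successes | Plan | Beta(0.5, 0.5) | Difference in lower limit |
|---|---|---|---|
| 16 | 0.660–0.926 | 0.627–0.913 | 0.032 |
| 17 | 0.717–0.955 | 0.686–0.944 | 0.031 |
| 18 | 0.780–0.979 | 0.750–0.971 | 0.030 |
| 19 | 0.851–0.996 | 0.820–0.991 | 0.031 |
| 20 | 0.953–1.000 | 0.910–1.000 | 0.043 |

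Under a uniform prior, 20 of 20 gives 0.867 to 0.998. Moving from 19 to 20 successes raises the difference from Beta(0.5, 0.5) by 0.043 − 0.031 = 0.012.

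**Step 4: how often the extreme case arises.** P(20 of 20) = 0.90^20 = 0.122 at the anticipated rate, and 0.95^20 = 0.358 if the true rate were 0.95, a value the document does not anticipate.

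**Step 5: what the interval decides.** Nothing. The rule compares x with 18. Results of 18, 19 and 20 are feasible, and 17 or fewer are not, under any prior.

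**Step 6: frequentist coverage, which the plan does not claim.** For a true rate p, coverage is the sum of the Binomial(20, p) probabilities over those x whose interval contains p.

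| True rate | Plan | Beta(0.5, 0.5) |
|---|---|---|
| 0.88 | 89.6% | 84.0% |
| 0.90 | 83.5% | 83.5% |
| 0.95 | 62.6% | 92.5% |
| average over 0.85–0.95 | 82% | 90% |
| average over 0.95–1.00 | 94.8% | 94.1% |
| average over 0.85–1.00 | 86% | 91% |

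The ranking changes with the true rate. At the anticipated 0.90 the two priors tie, and at 20 of 20 both intervals then miss the truth: 0.953 and 0.910 each lie above 0.90.

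**The case for a change.** The strongest argument does not need Beta(0.5, 0.5). Take priors that all share the sponsor's mean of 0.90. At 20 of 20 the lower limit is 0.972 under Beta(0.9, 0.1), 0.953 under the plan and 0.902 under Beta(9, 1). The lighter prior gives the more optimistic limit, so a weight of 2 patients is not in itself a reassurance. At 18 of 20 the same three priors give 0.777, 0.780 and 0.798, so the one worked example does not reveal this sensitivity. Reaching a lower limit of 0.953 would take 40 of 40 successes under Beta(0.5, 0.5) or 62 of 62 under a uniform prior. Coverage at a true rate of 0.95 is poor, and averaged over 0.85 to 1.00 it is below that of Beta(0.5, 0.5).

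All of these figures stand. They show that the lower limit after a perfect result depends on the prior. That is true of any Bayesian interval when no failures are seen, and the plan discloses the prior on which it depends. They do not show which prior is right. Beta(0.5, 0.5) is also unbounded at 1, and the difference is 0.043 or 0.086 (0.953 − 0.867) according to the yardstick chosen. The equivalents of 40 and 62 patients restate the same differences on a scale that stretches steeply near a rate of 1. Coverage favours one prior or the other according to the true rate assumed. Anyone who knows the count out of 20 can compute the interval under another prior, so nothing is concealed.

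**Conclusion.** The concern does not hold. The prior is pre-specified, agrees with its stated basis and reproduces the plan's own interval. The feasibility conclusion rests on a count that no prior can alter. What is left is a shift in the lower limit of 0.030 to 0.032 at 16 to 19 successes and 0.043 at 20, measured against a comparator that the document does not use. The largest shift belongs to a result with probability 12% at the anticipated rate. Adding an interval under a second prior would be a matter of preference in an exploratory study of this size; leaving it out does not make the planned result or conclusion wrong.

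This rests on three points: the interval is equal-tailed, as the worked example implies; all 20 patients are in the denominator; and the interval is read as a credible interval under the stated prior, without a claim of 90% frequentist coverage. It concerns the primary proportion only. The concordance analysis uses the same prior but was not examined here.

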# 1.0 Objectives

- 1. To determine the feasibility of acquiring *in-vivo* high-resolution microendoscopy (HRME) images of cervical adenocarcinoma *in situ* (AIS) immediately prior to conization.
- 2. To determine accuracy of HRME images in distinguishing AIS from normal cervical tissue.

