# High-Resolution Microendoscopy (HRME) Imaging:

A pilot study evaluating HRME imaging for pre-invasive cervical neoplasia was recently

performed in 174 women in rural China (16). All patients underwent HPV testing, VIA, colposcopy and HRME imaging. Of the 69 women noted to have abnormalities on colposcopy, only 12 (17%) showed high-grade disease on biopsy. However, HRME imaging correctly classified all 12 high-grade areas (100%) as abnormal, and correctly classified 38 of the remaining 57 (67%) as normal. Furthermore, when patients were stratified based on a positive high-risk HPV DNA test, HRME imaging correctly identified 100% of the patients with CIN2 or greater. Of the 30 patients with a positive high-risk HPV DNA test but no histologic evidence of disease, only 6 patients (20%) were incorrectly identified as abnormal on HRME imaging. These preliminary data suggest that HRME has improved specificity over VIA and colposcopy, potentially leading to more accurate identification of patients needing treatment as part of a See & Treat protocol. Our collaborative group also recently completed a pilot study comparing HRME to colposcopy and biopsy in 60 patients with cervical dysplasia at Barretos Cancer Hospital in Brazil with final data analysis pending.

Our group is also evaluating HRME for use in conservative, fertility-sparing surgery for women with endometrial cancer. We are evaluating if HRME can help distinguish tumor margins in women undergoing resection of the endometrial tumor without hysterectomy. We recently completed a prospective pilot study evaluating the use of HRME in patients with endometrial cancer. Following hysterectomy, the uterus was examined *ex-vivo* to identify whether HRME could distinguish between tumor and normal endometrium following the application of proflavine. Preliminary results show a 74% concordance rate between HRME and final pathology, which is significantly higher than the 59% concordance rate between gross evaluation and final pathology. A prospective trial evaluating HRME *in-vivo* in women with endometrial cancer was recently approved and accrual will begin in the near future.

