#### Rationale:

Cervical AIS is a significant pre-invasive disease that affects women of childbearing age. For women who desire future fertility, conservative management with cervical conization is considered a feasible option. However, the treatment is challenging as lesions are often located high in the endocervical canal, and are multicentric with "skip" lesions present. Repeat conizations must therefore be performed until negative margins are obtained. Given the microscopic nature of the disease, the surgeon typically cannot visually distinguish AIS from normal tissue in order to obtain negative margins. Furthermore, frozen section is difficult and inaccurate in assessing AIS margins. This lack of accurate intraoperative assessment results in 25-30% of patients undergoing one or more repeated conizations to obtain negative margins. In addition, an unnecessarily large specimen is sometimes removed in an attempt to be certain of obtaining negative margins. These large and repeat cervical conizations are known to be associated with adverse obstetrical outcomes, including preterm delivery and very low birth weight infants (17-19).

In order to overcome these challenges associated with the conservative management of AIS, we are proposing to use HRME, a novel cervical visualization technique, to evaluate epithelial cell morphology *in situ* in order to distinguish AIS from normal cervical tissue. *Our overall goal is to eventually use HRME to guide resection margins at the time of cervical conization for AIS*. Our *primary objective* is to determine the feasibility of acquiring *in-vivo* high-resolution microendoscopy (HRME) images of cervical adenocarcinoma *in situ* (AIS) immediately prior to conization. Our *secondary objective* is to determine accuracy of HRME images in distinguishing AIS from normal cervical tissue.

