## 4.0 Eligibility Criteria

## Inclusion Criteria:

- 1. Any woman with a confirmed preoperative diagnosis of cervical AIS, including co-existing squamous CIN and/or microinvasive cancer
- 2. Women undergoing cold knife cone (CKC) of the cervix at MD Anderson
- 3. Negative pregnancy test for women of child-bearing potential
- 4. Women who are >/= 21 years of age and < 65 years of age
- 5. Ability to understand and the willingness to provide informed consent and sign a written Informed Consent Document (ICD)

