#### 6.0 Research Plan and Methods

#### Treatment Plan:

The patient will be taken to the operating room and per standard practice, prior to converting the surgical area to a sterile field, an exam under anesthesia will be performed. Five percent acetic acid will be applied to the cervix. Routine colposcopy with visual inspection of the cervix for aceto-whitening will be performed and the findings noted. This will be followed by the topical application of 0.01% proflavine solution to the cervix. The HRME probe will then be applied to areas of the cervix that appear to be both normal and abnormal. High-resolution images will be obtained and the findings noted. Lugol's solution may then be applied to the cervix per standard practice and the findings noted. This may be followed by re-application of 0.01% proflavine solution to the cervix. The HRME probe will then be applied to areas of the cervix that appear to be both normal and abnormal. High-resolution images will be obtained and the findings noted.

The patient and surgical area will then be prepped in the typical sterile fashion. A cold knife cone biopsy will then be performed per standard practice. The investigational procedures are anticipated to add approximately 10 minutes to the patient's time in the operating room.

Immediately following the CKC, the removed surgical specimen will be evaluated. Proflavine will be reapplied to the surgical specimen and repeat evaluation with HRME performed and high-resolution images obtained. Small ink dots will be placed on the tissue surface at each area that was noted to be abnormal as well as normal areas, to enable co-registration of image sites with subsequent histopathology sections. The specimen will then be submitted to pathology for the usual pathological analysis.

A member of the research team will contact each participant within 30 days of the procedure to ask how they are feeling and if they are experiencing any of the symptoms mentioned under the risks and side effects section of the informed consent.

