## Data:

The protocol specific data collected will be stored in the Research Electronic Data Capture (REDCap) System/CORe.

Data collected will include the following, as well as all other protocol specific data:

- Age at diagnosis
- Histology
- Date of diagnosis
- Date of surgery
- Operative time
- Duration of time for intraoperative HRME imaging
- HRME imaging findings
- Final pathologic findings

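### The accuracy objective has one planned interval, for a concordance that cannot separate missed AIS from false alarms; sensitivity and specificity by inked site, with intervals allowing for clustering, should be prespecified

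*Combined protocol and SAP*

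**What the plan says.** Section 1.0 gives the second objective as: "To determine accuracy of HRME images in distinguishing AIS from normal cervical tissue".

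Section 10.0 plans two things for it, a table and one estimate: "We will tabulate AIS finding by the CKC specimen results as determined by pathology, and we will estimate the concordance of HRME images taken" ex vivo, and the sentence goes on "as described in section 6.0) with pathology findings with a 90% credible, assuming a beta (1.8, 0.2) prior distribution for the concordance". The word after credible is evidently meant to be interval. Sensitivity and specificity are not named, and the section does not say whether a unit is a site or a patient.

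The cross-reference leads to the Treatment Plan in section 6.0. There, ink dots go on the removed specimen at areas noted as abnormal "as well as normal areas, to enable co-registration of image sites with subsequent histopathology sections". No number of sites and no ratio of abnormal to normal sites is set.

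The Data list in section 6.0 names HRME findings and final pathology without saying at what level they are recorded, but it is open-ended: "Data collected will include the following, as well as all other protocol specific data".

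Section 4.0 admits "Any woman with a confirmed preoperative diagnosis of cervical AIS, including co-existing squamous CIN and/or microinvasive cancer". Section 10.0 does not say how CIN-only or microinvasive sites enter a comparison of AIS with normal tissue.

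**The concern.** The Rationale in section 3.0 states the purpose: "Our overall goal is to eventually use HRME to guide resection margins at the time of cervical conization for AIS". For that use the two errors have different consequences. A missed AIS site could leave disease behind, and a false alarm could mean removing more cervix than needed. Concordance adds the two errors together, so the only accuracy figure with stated uncertainty cannot show which kind the method makes. It also moves with the choice of sites even when the reader's performance is constant, which makes it hard to compare with other studies.

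Section 3.0 itself reports the earlier cervical pilot with the two rates apart: "HRME imaging correctly classified all 12 high-grade areas (100%) as abnormal, and correctly classified 38 of the remaining 57 (67%) as normal".

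A second, conditional issue is independence. Several sites are inked on each specimen. A single beta posterior over pooled sites treats them as independent, although sites from one patient share anatomy, staining and operator.

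**Working it through.** **1. The plan's own interval.** Section 10.0 states 0.78 to 0.98 for 18 of 20 under the same prior (primary objective). The posterior is Beta(1.8 + 18, 0.2 + 2) = Beta(19.8, 2.2), with 5th and 95th percentiles 0.780 and 0.979. This reproduces the stated interval and shows that it is equal-tailed. No numerical interval is given for accuracy. The same method is used below.

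**2. Concordance depends on site mix.** With π the share of AIS sites, concordance = π × sensitivity + (1 − π) × specificity. Take the pilot rates in section 3.0 (12/12 = 1.00 and 38/57 = 0.667). They concern high-grade lesions in general, so they serve only as an illustration.

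- Pilot's own mix, π = 12/69: (12 + 38)/69 = 0.72
- π = 0.5: 0.5 × 1.00 + 0.5 × 0.667 = 0.83
- π = 0.8: 0.8 × 1.00 + 0.2 × 0.667 = 0.93

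Conversely, different readers can score the same. Sensitivity/specificity of 0.95/0.50 and of 0.50/0.95 both give 0.725 at π = 0.5. For intervals, assume 80 sites (20 patients × 4), 40 AIS and 40 normal, with 64 concordant. The concordance is 0.80 (0.73 to 0.87) in each of these cases:

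| AIS sites correct | Normal sites correct | Sensitivity (90% interval) | Specificity (90% interval) |
|---|---|---|---|
| 36/40 | 28/40 | 0.90 (0.82 to 0.96) | 0.70 (0.59 to 0.82) |
| 24/40 | 40/40 | 0.60 (0.49 to 0.73) | 1.00 (0.98 to 1.00) |
| 40/40 | 24/40 | 1.00 (0.98 to 1.00) | 0.60 (0.49 to 0.73) |

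**3. If the unit were the patient.** Every patient enters with confirmed AIS. If all 20 cones show AIS, specificity has a denominator of 0 and its 90% interval is the prior alone, 0.49 to 1.00. With two AIS-free cones, both called correctly, it is 0.74 to 1.00.

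**4. If sites are pooled.** The documents give neither sites per patient nor the intraclass correlation (ICC), so both are assumed. The simulation has 20 patients, true concordance 0.75, and each patient's sites sharing one success rate. Coverage of the nominal 90% interval:

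| Sites per patient | ICC 0 | ICC 0.1 | ICC 0.2 | ICC 0.3 |
|---|---|---|---|---|
| 4 | 0.894 | 0.850 | 0.807 | 0.762 |
| 6 | 0.908 | 0.832 | 0.765 | 0.710 |
| 8 | 0.899 | 0.789 | 0.709 | 0.648 |

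At 2 sites per patient it is 0.82 to 0.86 over ICC 0.1 to 0.3. If patients differ only in the threshold for calling a site abnormal (50:50 sites, 4 to 8 per patient), concordance coverage is 0.87 to 0.93 at a true value of 0.75 and 0.76 to 0.89 at 0.90.

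**5. Width of the replacement.** At 75% correct:

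- 90/120 pooled sites: 0.686 to 0.814, width 0.128.
- 45/60 AIS sites, no clustering: 0.661 to 0.839, width 0.178.
- The same 60 sites, 3 per patient, assumed ICC 0.2: design effect 1 + 2 × 0.2 = 1.4, effective number 60/1.4 = 42.9, interval 0.646 to 0.854, width 0.208. At ICC 0.1 and 0.3 the widths are 0.194 and 0.221.

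So 0.178 − 0.128 = 0.050 comes from halving the sites, and 0.208 − 0.178 = 0.030 from clustering.

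**6. A patient-level bootstrap alone is not a safe replacement.** When every AIS site is called correctly, as in the pilot's 12/12, each resample is also 100% and the interval is 1.00 to 1.00. At an assumed true sensitivity of 0.98 (2 to 4 AIS sites per patient, ICC 0.1 to 0.3), nominal 90% coverage is 0.49 to 0.74, and 24% to 49% of samples are all correct.

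**The case against.** The strongest reply is that the plan already holds most of what is needed. It inks abnormal and normal areas, co-registers them with histology and promises a cross-table. If that table is made by site, misses and false alarms can be read off and the two rates follow by division. The study is exploratory, accuracy is secondary, and no decision rests on the concordance interval. This stands, and it limits the point: what is missing is the unit, the definitions and the intervals, not the ability to collect the data.

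A second reply is that clustering arises only if sites are pooled, which section 10.0 does not say. That is also true. The reference to section 6.0 points to the inked site without stating it, and the patient-level alternative has the problem shown in step 3.

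A reader might go further and infer that the planned interval is definitely too narrow. The documents do not support that. Coverage near 65% needs 8 sites per patient and an ICC of 0.3; with fewer sites, low correlation or a pure threshold shift it can be near nominal. A reader might also infer that site-level histology will not be recorded. The open-ended data list does not support that either; it is something to confirm.

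**Conclusion.** The point holds and is worth fixing. The accuracy objective has one planned interval, for a quantity that does not separate sensitivity from specificity. This follows from the text and from the definition of concordance and needs no assumption. On the protocol's own pilot rates, concordance would range from 0.72 to 0.93 as the share of diseased sites goes from 12/69 to 80%.

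The clustering part is conditional on pooling sites, and its size rests wholly on assumed site counts and ICCs. Only the statement that the interval may be too narrow is supported.

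The consequence is limited to the interpretation of an exploratory secondary analysis. It would be wrong to infer that the feasibility conclusion is affected: the 18-of-20 rule counts patients with successful in-vivo images and uses no concordance result.

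**What to change.** In section 10.0:

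- Name the inked ex-vivo site as the unit of analysis.
- From the planned table, report sensitivity among histologic AIS sites and specificity among histologic normal sites, each with a 90% interval that allows for clustering by patient. Use either a hierarchical beta-binomial model with stated priors, or a beta interval with the site count divided by a design effect, stating the ICC and how it was obtained. Do not rely on a patient-level bootstrap alone.
- Justify the prior for each rate. The present one rests on an anticipated 90% feasibility rate, and near 100% correct it largely drives the result (40/40 gives 0.98 to 1.00).
- Show CIN-only and microinvasive sites as separate rows.
- Keep concordance as a descriptive line.

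Confirm early that histology is recorded by inked site, since the rates may not be recoverable later if it is not.

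The cost is a few sentences and that check, with no extra patients or procedures. The downside is wider intervals, of the size shown in step 5, mostly because each rate uses only part of the sites.

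### The concordance interval has no stated unit or patient-level term; if inked sites are pooled and positively correlated within a cone, the nominal 90% interval is too narrow

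*Combined protocol and SAP*

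**What the plan says.** Section 10.0 fixes the unit for the primary objective. Feasibility is a proportion of patients, reported "with a 90% credible interval, assuming a beta(1.8, 0.2) prior distribution", and is declared if imaging succeeds in "at least 18 of the 20 patients enrolled in the study". For the secondary objective it says "we will estimate the concordance of HRME images taken" ex vivo, referring back to Section 6.0, "with pathology findings with a 90% credible, assuming a beta (1.8, 0.2) prior distribution for the concordance" (the word interval has evidently dropped out). It gives no unit, denominator, rule for combining sites or patient effect.

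Section 6.0 (Treatment Plan) describes how the ex-vivo data arise. After imaging of the removed cone, "Small ink dots will be placed on the tissue surface at each area that was noted to be abnormal as well as normal areas", and the purpose is "to enable co-registration of image sites with subsequent histopathology sections". Neither section says how many sites each cone will contribute.

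One sentence in Section 10.0 points towards a specimen-level reading: "We will tabulate AIS finding by the CKC specimen results as determined by pathology".

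**The concern.** A beta prior updated with a binomial count assumes independent observations. Sites on one cone share a patient, a staining and an imaging session. Section 10.0 also allows the imaging logistics to be adjusted after each cohort of 5, which could make agreement differ between patients. If agreement is positively correlated within a cone, 80 sites from 20 patients carry less information than 80 independent sites, and the simple interval does not show this.

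This interval is the only planned measure of uncertainty for one of the study's two objectives. Section 3.0 (Rationale) says the long-term aim is to guide resection margins, so overstated precision could carry into the planning of a later study. An unstated unit also leaves the denominator open until the data have been seen.

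**Working it through.** **Inputs from the documents.** 20 patients and a beta(1.8, 0.2) prior, with mean 1.8/2.0 = 0.90 and the weight of 2 observations (Section 10.0). Several sites per cone, number not given (Section 6.0). As one illustrative true concordance, 0.74, from the ex-vivo endometrial pilot in Section 3.0: "Preliminary results show a 74% concordance rate between HRME and final pathology". That is another organ, so it serves only as an illustration. The other illustrative value is the prior mean, 0.90.

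**Assumed.** m = 2, 4 or 8 sites per cone, equal across cones, and ICC from 0 to 0.5.

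**1. The plan's own figure.** For 18 of 20 patients the posterior is Beta(1.8 + 18, 0.2 + 2) = Beta(19.8, 2.2). Its 5% and 95% quantiles are 0.780 and 0.979, which reproduces the stated 0.78 to 0.98. The plan therefore uses the equal-tailed interval, and the same form is used below. No figure is given for concordance.

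**2. Width, by effective sample size.** Pooled n = 20m. Effective n = 20m / [1 + (m − 1) × ICC]. For m = 4 and ICC 0.3 this is 80 / (1 + 3 × 0.3) = 80 / 1.9 = 42.1.

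- At 0.90 observed, pooled: Beta(1.8 + 72, 0.2 + 8) = Beta(73.8, 8.2), giving 0.841 to 0.948.
- At 0.90 observed, effective n 42.1: 0.817 to 0.962, which is 1.35 times as wide.
- At 0.74 observed: 0.662 to 0.819 pooled and 0.635 to 0.847 adjusted, again 1.35 times as wide.

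**3. Coverage of the pooled nominal 90% interval.** The total agreement count x is the sum of 20 independent beta-binomial(m, mean p, ICC) counts. Its exact distribution comes from convolution. The interval is the equal-tailed 90% range of Beta(1.8 + x, 0.2 + 20m − x). Coverage is the probability that it contains p.

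| True p | Sites per cone | ICC 0 | ICC 0.1 | ICC 0.3 | ICC 0.5 |
|---|---|---|---|---|---|
| 0.74 | 2 | 0.888 | 0.871 | 0.836 | 0.804 |
| 0.74 | 4 | 0.868 | 0.813 | 0.724 | 0.656 |
| 0.74 | 8 | 0.891 | 0.781 | 0.636 | 0.547 |
| 0.90 | 2 | 0.878 | 0.859 | 0.821 | 0.787 |
| 0.90 | 4 | 0.885 | 0.834 | 0.746 | 0.677 |
| 0.90 | 8 | 0.884 | 0.771 | 0.621 | 0.529 |

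The ICC 0 column is the baseline, and its small shortfall from 0.90 is not due to clustering. Against it, the loss at 2 sites and ICC 0.1 is 0.888 − 0.871 = 0.017 at p = 0.74 and 0.878 − 0.859 = 0.019 at p = 0.90.

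**4. A case in which errors offset.** Suppose half the sites on each cone are AIS and half normal, and patients differ only in reading threshold: sensitivity Φ(c + u), specificity Φ(c − u), u normal with SD 0.5, 1.0 or 1.5 on the probit scale. With 2 or 4 sites, coverage is 0.887 to 0.945 at p = 0.74 and 0.853 to 0.899 at p = 0.90. With 8 sites it is 0.905 / 0.899 / 0.868 at p = 0.74 and 0.882 / 0.825 / 0.761 at p = 0.90.

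**5. An interval that respects the patient.** A hierarchical beta-binomial model with beta(1.8, 0.2) on the mean and a uniform(0,1) prior on the ICC was simulated 5,000 times per setting. At ICC 0.3 it covers 0.895 (p = 0.74) and 0.907 (p = 0.90) with 4 sites, and 0.903 and 0.914 with 8 sites.

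**The case against.** The strongest reply is that what the text shows is an unstated unit, and that under-coverage follows only if sites are pooled, each cone has several sites, and the net correlation within a cone is positive. Section 10.0 can be read as one result per cone: it tabulates by specimen result and reuses the prior of the patient-level endpoint. With one result per cone there is no clustering to correct.

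Part of this stands. The per-cone reading is not excluded. The site reading is nevertheless the more natural one. The concordance sentence refers to the images of Section 6.0, which are matched to histology site by site. Moreover, Section 4.0 admits only women with confirmed AIS, so the normal comparison must come mainly from normal areas of the same cones.

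Positive correlation is also not established. Each cone supplies both normal and abnormal areas, so a patient-specific reading threshold can produce errors that offset. Step 4 shows that little coverage is then lost with 2 or 4 sites, though not with 8 sites at high concordance and large threshold variation.

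A reader might infer from the table that the planned interval is known to cover 0.53 to 0.87. The documents do not support that, because they give neither a site count nor an ICC. The table is a range under assumptions and not a property of the plan.

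**Conclusion.** The concern holds in conditional form. Section 10.0 names no unit and no patient-level term for concordance. If inked sites are pooled and agreement is positively correlated within a cone, the nominal 90% interval is too narrow. With 20 cones, equal site counts and true concordance of 0.74 or 0.90, coverage falls from about 0.87 (2 sites, ICC 0.1) to 0.53 (8 sites, ICC 0.5), with 0.72 to 0.75 at 4 sites and ICC 0.3. The loss is slight with few sites and weak correlation, and mostly small if errors offset within cones.

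A reader might also take this as a threat to the study's conclusion. It is not: the objective is secondary, the study is exploratory, no decision rule uses concordance, and the feasibility rule with its 0.78 to 0.98 interval is counted by patient and unaffected. The point is worth making because the correction is cheap. Confidence is moderate, since the size depends on quantities that the documents do not give.

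**What to change.** State in Section 10.0 that the inked site is the unit for concordance and the patient is the cluster. Take the 90% interval from a method that respects the patient, and report the number of sites per cone. One example is a hierarchical beta-binomial model with beta(1.8, 0.2) on the mean and an ICC prior fixed in advance. If one result per cone is intended instead, say so and give the rule that combines a cone's sites.

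The cost is two or three sentences and minor analysis work, with no extra patients or procedures. The example model has drawbacks:

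- **Wider interval.** At 4 sites and ICC 0.3, mean width is about 0.21 against 0.155 at true 0.74, and 0.144 against 0.103 at true 0.90.
- **Mildly conservative without clustering.** Coverage is 0.94 to 0.96 with 4 or 8 sites.
- **Little gain with few sites.** At 2 sites, ICC 0.3 and true 0.90, coverage is about 0.845 against 0.82.
- **Incomplete repair under strong clustering.** At ICC 0.5 and true 0.90, coverage is 0.83 / 0.87 / 0.88 with 2 / 4 / 8 sites.
- **Dependence on the ICC prior.** With beta(1, 3) in place of uniform(0,1), at 4 sites and ICC 0.3, coverage is 0.881 against 0.895 at true 0.74 and 0.858 against 0.907 at true 0.90. The prior must therefore be set before the data are seen.
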